8.4 Phase 4: Follow-Up and Study Exit

The follow-up period begins after the study procedure session. Subjects will undergo follow-up visits at **2 weeks**, **4 weeks**, **12 weeks**, **26 weeks and 52 weeks**, calculated from the study procedure date. Visits should be scheduled within the visit windows specified in Table 1. Requirements for each follow-up visit are described in Section 8.5 and shown in Table 1.

Subjects meeting the study requirements as planned will be exited from the study at the 52-week follow up visit. If a subject reaches the 52-week follow-up visit and is experiencing a new or ongoing adverse event, the study sponsor should be contacted to discuss the need and/or methods for continued surveillance of the event.

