Study-Specific Quality of Life (QOL) Questionnaire – The QOL questionnaire will be used to gain understanding of the impact of chronic rhinitis on the subject's daily activities, feelings, symptoms and medication use. The QOL will be completed by the subject both prior to the treatment procedure, and at the 12-week, 26-week and 52-week follow-up visits.

Subject Satisfaction Survey – The Satisfaction Survey will be used to assess patient acceptance of the treatment procedure and results. Subjects will be asked to complete the Satisfaction Survey at the 12-week and 52-week follow-up visits.

Adverse Event Evaluation – Subjects will be asked about possible side effects or adverse experiences related to the study procedure. All events will be documented on the Adverse Event Log and Adverse Event Case Report Form. Anticipated observations related to the study procedure will be tabulated but will not be categorized as adverse events unless they require mitigation by the treating physician or are greater in severity, duration or degree of incidence than anticipated. Refer to Table 2 for a listing of anticipated observations as well as anticipated frequency, severity and duration.

Medications – Updates to current medications and any new or changed medications will be requested at each follow-up visit. The medication log will be updated to reflect any changes. In addition, any medications required as a result of intervention related to the study procedure will be documented and correlated with the Adverse Event Case Report Form.

Table 1 outlines the assessments to be performed at each required visit and specifies the required visit windows.

TP668 Ver. 27-NOV-2018

Assessments	Screening / Baseline	Study Procedure (within 4 weeks of Baseline visit)	Immediately Post- Treatment	2-Week Follow-Up (+/- 3 days)	4-Week Follow-Up (+/- 1 week)	12-Week Follow-Up (+/- 2 weeks)	26-Week Follow-Up (+/- 3 weeks)	52-Week Follow-Up (+/- 4 weeks)
Demographics and Medical History	Х							
Physical Exam and Vital Signs	Х							
Medication Review	Х	Х		Х	Х	Х	Х	Х
Study Procedure		Х						
Endoscopic Assessment of treatment area (with video or photo capture)	Х	X*	X*	Х	Х	Х	Х	Х
rTNSS Score	Х			Х	Х	Х	Х	Х
Subjective Pain VAS			Х	Х	Х	Х		
QOL Questionnaire	Х					Х	Х	Х
Subject Satisfaction Survey						Х		Х
Adverse Event review			Х	Х	Х	Х	Х	Х
Pregnancy test (if female)		Х						

*Endoscopic assessment to be done both immediately prior to and after procedure

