12.1 Potential Risks

Potential risks associated with the use of the InSeca ARC System do not differ from those of the commonly used devices and procedures to treat chronic rhinitis discussed previously, but due to the non-surgical nature of the therapy, small treatment area, low-power delivery and lack of need for general anesthesia, the overall risk to the patient may be less than from other procedures such as vidian neurectomy, septoplasty and/or functional rhinoplasty.

Potential risks associated with the use of the InSeca System and/or the associated local anesthetics are outlined below. Subjects will be monitored closely as part of this study to allow for detection of symptoms, should they be present. This, in turn, should allow for early treatment or intervention, if necessary.

The following are adverse events or side effects that may occur as a result of the treatment:

- Infection
- Bleeding (other than intra-treatment at treatment sites and greater than anticipated by the investigator)
- Mucosal changes
- Scar formation leading to nasal obstruction •
- Sensory changes at treatment site •
- Dry eye •
- External swelling of nose •
- Vasovagal response secondary to the procedure •
- Change in external shape or appearance of nose •

The following two tables list anticipated observations that are expected in and around the treatment Table 2 provides the incidence (reported as percentage of treated nostrils) observed in area. Clinical Study TP258, the nasal valve pivotal study. Table 3 provides the incidence observed in Clinical Study TP220, the rhinitis feasibility study. Anticipated observations will be assessed and recorded at study visits if they occur but, being anticipated as a result of the procedure, will not be considered adverse events unless they require mitigation by the treating physician or are greater in severity, duration or degree of incidence than anticipated. If one of these types of observations is deemed to be an adverse event, it should be recorded on the study Adverse Event CRF.

Observation	Post-Procee (% treated ne n = 99)	dure ostrils	4-Week Follow-Up (% treated nostrils n = 99)		12-Week Foll (% treated no n = 99)	ow-Up ostrils	26-Week Foll (% treated no n = 96)	ow-Up ostrils
Inflammation / redness	Not present Mild Moderate	53 42 5	Not present Mild Moderate	79 17 4	Not present Mild Moderate	89 9 2	Not present Mild Moderate	89 10 1

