Swelling, edema	Not present Mild Moderate	45 52 3	Not present Mild Moderate	75 24 1	Not present Mild Moderate	89 9 2	Not present Mild Moderate	89 8 3
Nasal obstruction from tissue edema	Not present Mild Moderate	76 23 1	Not present Mild Moderate	82 13 5	Not present Mild	94 6	Not present Mild Moderate	90 9 1
Disruption of mucosal flow / crusting	Not present Mild Moderate	89 10 1	Not present Mild Moderate	62 34 4	Not present Mild Moderate	84 15 1	Not present Mild Moderate	91 8 1
Blanching	Not present Mild Moderate	29 58 13	Not present Mild	98 2	Not present Mild	98 2	Not present	100
Numbness	Not present Mild Moderate	56 30 14	Not present	100	Not present	100	Not present	100
Soreness, pain	Not present Mild Moderate	70 29 1	Not present Mild	94 6	Not present Mild	99 1	Not present	100
Bleeding at anesthetic injection site (no intervention)	Not present Mild Moderate	51 47 2	Not present	100	Not present	100	Not present	100
Bleeding at treatment site (no intervention)	Not present Mild	85 15	Not present	100	Not present	100	Not present	100
Saddle nose deformity	Not present	100	Not present	100	Not present	100	Not present	100
Bruising around orbital area	Not present	100	Not present	100	Not present	100	Not present	100

Table 2. Treatment Area Observations – TP258 Nasal Valve Pivotal Clinical Study

Table 3. Treatment Area Observations - TP220 Rhinitis Feasibility Clinical Study

Observation	Baseline (% treated nostrils n = 22)	Baseline2-Week Follow-Up $\%$ treated nostrils(% treated nostrils $n = 22$) $n = 20$)		1-Month Follo (% treated no n = 16)	ow-Up strils	3-Month Follow-Up (% treated nostrils n = 8)	
Swelling, edema	Not present9Mild91	Not present Mild	75 25	Not present Mild Not reported	75 12.5 12.5	Not present Mild	75 25
Blanching / color of mucosa	Pale pink 100	Pale pink Hyperemic	90 10	Pale pink	100	Pale pink Not reported	75 25
Obstruction	Not present91Present beyondmid-Meatus9	Not present Present in Ethmoid	90 10	Not present	100	Not present	100
Discharge	Not present45.4Thin36.4Thick18.2	Not present Thin Thick	60 35 5	Not present Thin	87.5 12.5	Not present Thin	87.5 12.5
Scarring / Crusting	Not present 91 Mild 9	Not present Mild Severe	35 50 15	Not present Mild	62.5 37.5	Not present	100

TP668 Ver. 27-NOV-2018

CONFIDENTIAL

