13.11 Primary Safety Endpoint Analysis

Safety will be assessed by characterizing the type and frequency of adverse events reported at or following the study procedure, and throughout the follow-up period. Event types include:

- Serious Adverse Events, including Deaths
- Serious Adverse Device Effects
- Unanticipated Adverse Device Effects
- Device Related Serious Adverse Events

The number of events as well as the percentage of subjects experiencing each event type will be calculated.

All adverse events will be analyzed for all enrolled subjects. Adverse events will be coded using a standardized dictionary, so that adverse events may be categorized for analysis at an appropriate level of detail. Listings will be provided to detail individual events. The number of subjects, number of adverse events, and the proportion of subjects reporting each adverse event will be summarized. Seriousness and severity of adverse events and their relationship to the device and/or procedure will be summarized. A time course of adverse events will be presented using the intervals:

- 0 days to 2 weeks
- 2 weeks to 4 weeks
- 4 weeks to 12 weeks
- 12 weeks to 26 weeks
- 26 weeks to 52 weeks

Narratives will be presented for all deaths, serious adverse events, serious adverse device effects, unanticipated adverse device effects, and subjects withdrawn due to an adverse event.

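### Sections 8.5 and 12.1 use different benchmarks for anticipated observations, so unmitigated severe scarring/crusting at 2 weeks is an adverse event under one and not under the other

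*Combined protocol and SAP*

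**What the plan says.** Section 12.1 (Potential Risks) introduces Tables 2 and 3 together: "The following two tables list anticipated observations that are expected in and around the treatment" area. It then exempts these observations from adverse event status. They "will not be considered adverse events unless they require mitigation by the treating physician or are greater in severity, duration"; incidence is named as a further ground, and each is judged against what was anticipated. There are thus four routes into the adverse event count: mitigation, greater severity, longer duration and higher incidence.

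Section 8.5 (Types of Assessments, Adverse Event Evaluation) repeats the exemption: "Anticipated observations related to the study procedure will be tabulated but will not be categorized as adverse events" unless the same conditions are met. For the benchmark it names one table only: "Refer to Table 2 for a listing of anticipated observations as well as anticipated frequency, severity and duration".

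Table 2 comes from the nasal valve study TP258 and Table 3 from the rhinitis feasibility study TP220. In Table 3, the scarring/crusting row at the 2-week visit has the levels "Not present Mild Severe", at 35%, 50% and 15% of 20 nostrils. Table 2 has no severe grade for any observation at any visit.

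Section 13.11 defines the primary safety endpoint through adverse events: "Safety will be assessed by characterizing the type and frequency of adverse events reported at or following the study procedure" and through follow-up. Section 11.0 requires a relatedness judgement, onset date, severity and duration for each adverse event, and monitoring until it is resolved or explained. The adverse event definition in Section 31.0 covers any untoward medical occurrence and makes no exception for anticipated observations.

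**The concern.** The exemption works only if investigators know what was anticipated, and the two sections that state it give different answers. A site following 8.5 would report an unmitigated severe crust at 2 weeks as an adverse event; a site following 12.1 would not. The count that forms the primary safety endpoint would then depend partly on which section the site read.

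Under 12.1 there is a second problem. Where the table already holds the highest grade shown, the severity condition cannot be met, and the physician's decision to intervene becomes in practice the only way to an adverse event. Sites that intervene less would report fewer events for the same endoscopic finding.

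**Working it through.** **Step 1: reproduce the Table 3 cell.** With n = 20 nostrils: 0.35 × 20 = 7 not present, 0.50 × 20 = 10 mild, 0.15 × 20 = 3 severe, total 20. The exact (Clopper-Pearson) 95% interval for 3/20 runs from the 0.025 quantile of Beta(3, 18) to the 0.975 quantile of Beta(4, 17), that is 3.2% to 37.9%. It treats nostrils as independent, so it is if anything too narrow.

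**Step 2: apply the rule to one subject with unmitigated severe scarring/crusting at 2 weeks.**

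| Condition | Benchmark under 8.5 (Table 2) | Benchmark under 12.1 (Tables 2 and 3) |
|---|---|---|
| Mitigation | not met | not met |
| Severity | met: crusting is at most moderate at every visit (1%, 4%, 1%, 1%) | not met: severe is already listed, and no higher grade is shown |
| Duration | not needed | not met: the finding is at the visit where the table lists it |
| Incidence | not needed | a percentage of nostrils in a group; cannot readily classify one subject |
| Result | adverse event | not an adverse event |

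Table 2 has no 2-week column, but since none of its cells is severe, any interpolation gives the same result.

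**Step 3: illustrative size.** Assume the 15% per-nostril rate recurs and all 50 planned subjects, treated in both nostrils, attend at 2 weeks.

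- Nostrils always alike: 50 × 0.15 = 7.5 subjects.
- Nostrils independent: 50 × (1 − 0.85²) = 50 × 0.2775 = 13.9 subjects.
- At the interval limits: 50 × 0.032 = 1.6 (alike, lower limit) to 50 × (1 − 0.621²) = 30.7 (independent, upper limit).

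These are subjects with the finding. Those whose finding is mitigated become adverse events anyway, and the documents give no mitigation rate. At a given rate, the figures are therefore ceilings on the number left out.

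**Step 4: moderate findings at 26 weeks.** Table 2 (n = 96 nostrils) shows moderate inflammation 1%, swelling 3%, obstruction from edema 1% and crusting 1%, or about 1, 3, 1 and 1 nostrils. Per 50 subjects:

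- 1% items: 50 × 0.01 = 0.5 to 50 × (1 − 0.99²) = 1.0.
- Swelling: 50 × 0.03 = 1.5 to 50 × (1 − 0.97²) = 3.0.

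Moderate persistence to that visit can be read as anticipated. One cell differs: at 12 weeks Table 2 shows obstruction as 94% not present and 6% mild, so moderate obstruction then exceeds it.

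**Step 5: where the conditions still work.**

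- Severe inflammation, swelling or obstruction exceeds both tables at every visit.
- Severe crusting after 2 weeks exceeds both: Table 3 has 0 of 16 severe at 1 month, and Table 2 has at most moderate.
- "Subjects meeting the study requirements as planned will be exited from the study at the 52-week follow up visit", while Table 2 ends at 26 weeks and Table 3 at 3 months, so later persistence exceeds both.

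**The case against.** The best defence is that nothing is hidden. Anticipated observations are tabulated under 8.5, and 13.12.1 summarizes every level of each nasal status component at baseline and each follow-up. The primary safety endpoint is descriptive, with no threshold or test, so no formal conclusion can reverse. Section 12.1 also names mucosal changes and scar formation leading to obstruction among possible adverse events or side effects, which gives an investigator grounds to report a bad scar. All of this is correct and limits the harm. But tabulation under other safety analyses does not bring a relatedness judgement or monitoring to resolution, and the overlap within 12.1 adds to the ambiguity.

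A second objection is that each gap needs a particular table. With Table 2 alone, the severity gap disappears; with Table 3 alone, there is no 26-week column. That is also true, but 12.1 as written uses both, and the disagreement with 8.5 is itself the defect.

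A third is that the rate may not carry over. TP220 applied energy to the inferior turbinate (Section 5.0), and three nostrils are few. The tables also give prevalence by visit, not how long any one event lasted. This stands against the size, which is illustrative, but not against the classification problem.

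**Conclusion.** The two sections need to be reconciled. Under 12.1, unmitigated severe scarring/crusting at 2 weeks stays out of the adverse event count; under 8.5 it goes in. This rests on taking severe as the top grade, since the protocol shows none higher and leaves the specific observations to the case report form. The 7.5 to 13.9 of 50 subjects holds only if three nostrils' worth of earlier experience repeats. The 26-week gap for moderate findings is real but small.

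A reader might infer that the severity and duration conditions are inoperative throughout the tables, so that severe or persistent findings generally escape. The documents do not support this. Moderate is not a ceiling where severe exists as a grade, and persistence beyond 26 weeks is outside both tables. Nor should the 9% to 11% of nostrils per item with any inflammation, swelling, obstruction or crusting at 26 weeks be taken as the size of the problem: most of those findings are mild.

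**What to change.** Put one identically worded rule in 8.5 and 12.1, naming the same benchmark table or tables. State in both that any treatment-area observation graded severe at any post-treatment visit is recorded as an adverse event, whether or not it was mitigated and whatever the tables show.

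In 13.11, next to the adverse event table, report at each visit the number of subjects with a moderate or worse observation above their own baseline grade. This covers the 26-week gap without a fixed week from which moderate findings must count as adverse events, a cut-off for which the documents offer no basis.

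The cost is protocol and case report form wording, a few more adverse event forms and one extra summary. Endoscopic assessment is already scheduled at baseline and every follow-up visit, so no new data are needed. The reported adverse event rate will be somewhat higher.

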12.2 Potential Benefit

Potential benefit, associated with the use of the InSeca System, is to offer a safe, minimally invasive treatment method to alleviate the symptoms of chronic rhinitis.

12.3 Minimization of Anticipated Risks

Risks associated with the InSeca ARC System are minimized by design. In addition, risks will be minimized through the use of an Investigator with a high degree of experience in nasal surgical and minimally invasive procedures. The Investigator will receive sponsor-led training in proper use of the device prior to study initiation and as warranted throughout the study. The sponsor will monitor the study for any trends that would indicate a safety issue.

12.4 Potential Risks to Patient Confidentiality

In all clinical studies, confidentiality of protected health information may be breached due to studyrelated activities beyond those of routine clinical care. This risk will be minimized by not collecting personally identifying information on Case Report Forms (CRFs) or other study-related documentation to be provided to the study sponsor.

13.0 STATISTICAL CONSIDERATIONS

13.1 Study Design

This study is a prospective, multicenter, nonrandomized, nonsignificant risk (NSR) study of the Aerin Medical InSeca ARC Stylus when used to treat tissue in the posterior nasal nerve area to improve symptoms in those diagnosed with chronic rhinitis. Each subject serves as their own control for comparing baseline condition with postintervention condition.

The design encompasses a 2-phase enrollment. Up to 10 subjects will be enrolled in the first phase. Further enrollment will be suspended until all initial subjects have completed their 4-week evaluation. Information from these patients will be used to assure the safety of the procedure as well as the adequacy of treatment settings and treatment locations. The standard deviation of the change in TNSS score will be used to gauge the appropriateness of the assumption of standard deviation used for study sample size estimation.

13.2 Study Hypothesis

The primary endpoint of the study is change in mean rTNSS score from baseline to the 12-week evaluation. Improvement in the rTNSS score is represented by a decrease from baseline in the 12-point score. The minimum clinically important difference (MCID) for change in mean TNSS score derived from anchor-based methodologies has been shown to be 0.23 - 0.28 units and by distribution-based methodology the MCID was 0.59 units.²⁰ A less rigorous expert panel-based estimate of the MCID was 30% of the maximum score of 12, which is 3.6 units.²¹ The evidence-based thresholds for MCID have been recommended to supersede the panel-based method.^{22,23} An MCID of 1 unit, or 2 to 4 times the more rigorously derived MCIDs, was set for this study.

The hypothesis is that the improvement (decrease) in rTNSS mean score, measured as change from baseline at 12 weeks (12 weeks - baseline), exceeds the MCID (1 unit).

13.3 Sample Size Estimate

Sample size estimation was based on a paired t-test for change from baseline at 12 weeks using the following assumptions:

- Significance level $\alpha = 0.05$ (one-sided)
- Power = 90%
- MCID = 1-point decrease in mean change score = the minimum clinically important difference
- μ_d = -2-point decrease in mean change score = the minimum expected observed difference
- SD = 2 = the expected standard deviation of the observed mean difference
- 10% dropout and nonevaluable.

The minimum number of subjects to achieve 90% power is 36 (G-Power, paired t-test).

The overall planned study sample size is 50 subjects. Fifty subjects allows for the possibility that findings from the review of the phase-1 initial subjects, with respect to the planned protocol treatment parameters, leads to significant protocol modifications to the procedure parameters for the remainder of the subjects. Significant modifications would exclude the initial subjects from the primary endpoint analysis, but a sufficient number of subjects would remain for analysis of the primary study hypothesis.

The sample size estimate will be re-evaluated after the standard deviation of the mean change for the phase-1 initial subjects has been obtained. If the observed standard deviation is larger than the assumed standard deviation, the sample size may be recalculated to assure adequate study size to evaluate the study hypothesis. This evaluation will not be an efficacy evaluation and will not be used to halt the study based on an early determination of success or to decrease the planned sample size.

13.4 Definition of Populations

Enrolled Population – all subjects enrolled in the study.

Evaluable Population – all subjects that are enrolled in the study and have received the study procedure. If a protocol revision is required after review of the initial subjects that substantially alters the treatment settings, a subgroup of the evaluable population will be defined to include only those subjects enrolled and treated under the revised protocol (revised protocol population). Results will be summarized for the evaluable population, the initial protocol population, and the revised protocol population (used for primary endpoint analysis).

Safety Population – all subjects that have received the study procedure

13.5 Missing Data

All efforts will be made to collect all data points in this study. The study hypothesis will be tested using all available data for the subjects in the evaluable patient population. If the primary endpoint is not available for all such subjects, then sensitivity analysis will be performed to assess the potential effect of missing data on the study conclusion. The sensitivity analysis will be performed by imputing all missing data points for the primary endpoint as no (0) improvement. If the study conclusion is upheld using this type of worst-case scenario, no other analysis will be performed. However, if the conclusion using imputed data is different, a multiple imputation approach may be used to gain further insight to the results.

